[figure not shown]

Pilot Study: Investigating a Novel Supplement-based Therapy for the Treatment of Small Intestinal Bacterial Overgrowth

[name].
Senior Director, Scientific Affairs at Atrium Innovations

Version #2
May 3, 2017

Study Synopsis

The aim of this pilot study is to determine the efficacy of a supplement protocol combined with a low FODMAP diet for the treatment of small intestinal bacterial overgrowth (SIBO). The study is designed as a prospective, open label investigation, with an estimated sample size of 10 patients.

Patients diagnosed with SIBO by [name] at Good Medicine Clinic (Oxford, Ohio) will be offered the opportunity to enroll in this study, if they satisfy the inclusion and exclusion criteria upon initial diagnosis. No control group will be assigned.

The diagnosis of SIBO will be determined via assessment of clinical symptoms and the results of a lactulose breath test. This diagnosis procedure is, currently, the standard-of-care. After administration of the supplement therapy and adherence to a low FODMAP diet (8 weeks), the lactulose breath test will be repeated and symptoms re-assessed by [name].

The post-treatment lactulose breath test and all supplements in the protocol will be provided free-of-charge to enrolled patients. In addition, enrolled patients will not be billed for the mid-treatment office visit. Patient and/or patient insurance will be responsible for all other expenses, including but not limited to the initial breath test, all other office visits and travel.

Background

Small intestinal bacterial overgrowth (SIBO) is a category of gastrointestinal infection, characterized by an increased concentration ($>100,000$ CFU/mL proximal jejunal fluid) of bacteria in the small intestine.¹ Symptoms of SIBO commonly afflict the gastrointestinal tract and include but are not limited to: abdominal pain, discomfort, bloating, cramping, flatulence, diarrhea, constipation, eructation, and low serum B12.^{3,4}

SIBO is believed to be severely under diagnosed and is associated with numerous comorbid conditions including irritable bowel syndrome, diabetes mellitus and hypothyroidism.^{4,5} Small-bowel aspiration (SBA) or breath tests are used to aid in the diagnosis of SIBO. Due to the cost and invasive nature of SBA, glucose or lactulose breath tests are more commonly performed.

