Visit -1 [name] will assess patient history and symptoms, at his facility in Oxford, Ohio. If suggestive of SIBO, a lactulose breath test will be prescribed. Additional testing may be performed, at the discretion of [name], to aid in the initial diagnosis of the patient.

Visit 0 [name] will assess the results of the breath test and confirm or deny the diagnosis of SIBO. Treatment options for SIBO will be discussed, and the patient will be made aware of this investigation as a theoretical treatment option. Patient eligibility will be determined by [name] who will complete the Patient Eligibility Checklist (Appendix A) for each patient. All female patients will be asked to complete a urine pregnancy test to confirm pregnancy status. Eligible patients will be asked to review

and sign the Informed Consent document. [name] (Medical Assistant at Good Medicine) will be available to discuss patient consent and confidentiality. Enrolled patients will be asked to complete a baseline Medical Symptom Questionnaire (Appendix B). Afterwards, [name] will review the supplement therapy (Supplement Overview - Appendix C) and low FODMAP diet (Low FODMAP Handout - Appendix D). Patients will then be provided with all supplements necessary to complete the investigation. Patients will be asked to discontinue all other supplements during the study. However, no wash out period is required. Prescription medications, over-the-counter medications and/or supplements deemed medically necessary by the patient's primary care physician and/or [name] may be continued, if there are no known contraindications.

Visit 1 Visit 1 will occur approximately 4 weeks after the patient begins the supplement protocol. Patients will be asked to report their compliancy with the supplement protocol and low FODMAP diet and describe adverse effects. Patients will also be asked to complete the Medical Symptom Questionnaire. Patients will be provided with the second lactulose breath test kit and instructed to perform the test within 2 weeks of completing the supplement therapy.

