Visit 2 Visit 2 will occur after the results of the post-treatment breath test are available. [name] will interpret the results of the second breath test, and patients will be asked to complete the Medical Symptom Questionnaire, report compliancy with the supplement protocol and low FODMAP diet, and describe any adverse effects. Further treatment options will be discussed if necessary; follow-up treatment will be outside the scope of this investigation.

Risk/Safety Information

This study presents risk in the form of adverse reactions to ingredients in the supplement therapy. Patient risk will be minimized by excluding patients who may respond poorly to the supplement therapy or testing procedures from the study, i.e., by abiding by the aforementioned patient enrollment exclusion criteria.

Monitoring/Reporting

Patients may report adverse events to Good Medicine during scheduled office visits or by phone during office hours. If serious or life-threatening side effects arise, patients are instructed to call 911. Possible side effects include but are not limited to: diarrhea, constipation, nausea, vomiting, bloating or headache. When necessary, [name] or [name] will communicate with patients outside the office by phone and record adverse events in the patient's confidential files. Medical guidance will be provided as necessary.

Study Oversight

This study will be terminated if one-half or more of enrolled patients withdraw due to adverse events. [name] and [name] (Senior Director, Scientific Affairs at Atrium Innovations) will monitor, determine the need for and facilitate the termination of the study. Direct access to study related data will be made available for monitoring, auditing, IRB review and regulatory inspection.

Data Management

Lactulose breath test scores and completed Medical Symptom Questionnaire will be compared pre- and post-treatment to determine the efficacy of the supplement therapy. The significance of the change in breath test scores will be determined if the final sample size permits such analysis.

IRB Review/Ethics/Informed Consent

This study will be conducted in accordance with the ethical principles that have their origin in the Declaration of Helsinki and that are consistent with Good Clinical Practice and applicable regulatory requirements.

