Appendix B

The MSQ will be administered online via the Living Matrix platform. The following is a print copy of the questionnaire. Instructions to access the Living Matrix will also be provided to patients. This document was submitted to Schulman as an additional file.

Living Matrix MSQ

Please answer EVERY QUESTION in this section. Select "Zero" if you do not have this symptom.

Rate the Symptom

- Headache
- 0 - Never or almost never have the symptom
 - 1 - Occasionally have it, effect is not severe
 - 2 - Occasionally have it, effect is severe
 - 3 - Frequently have it, effect is not severe
 - 4- Frequently have it, effect is severe

- Faintness
- 0 - Never or almost never have the symptom
 - 1 - Occasionally have it, effect is not severe
 - 2 - Occasionally have it, effect is severe
 - 3 - Frequently have it, effect is not severe
 - 4- Frequently have it, effect is severe

- Dizziness
- 0 - Never or almost never have the symptom
 - 1 - Occasionally have it, effect is not severe
 - 2 - Occasionally have it, effect is severe
 - 3 - Frequently have it, effect is not severe
 - 4- Frequently have it, effect is severe

- Insomnia
- 0 - Never or almost never have the symptom
 - 1 - Occasionally have it, effect is not severe
 - 2 - Occasionally have it, effect is severe
 - 3 - Frequently have it, effect is not severe
 - 4- Frequently have it, effect is severe

Eyes

Rate the Symptom

Rate the Symptom

Watery or itchy eyes

- 0 - Never or almost never have the symptom
- 1 - Occasionally have it, effect is not severe
- 2 - Occasionally have it, effect is severe
- 3 - Frequently have it, effect is not severe
- 4- Frequently have it, effect is severe

Swollen, red or sticky eyelids

- 0 - Never or almost never have the symptom
- 1 - Occasionally have it, effect is not severe
- 2 - Occasionally have it, effect is severe
- 3 - Frequently have it, effect is not severe
- 4- Frequently have it, effect is severe

Bags or dark circles under eyes

- 0 - Never or almost never have the symptom
- 1 - Occasionally have it, effect is not severe
- 2 - Occasionally have it, effect is severe
- 3 - Frequently have it, effect is not severe
- 4- Frequently have it, effect is severe

Blurred or tunnel vision-does not include near or far-sightedness

Ears

Rate the Symptom

Itchy ears

- 0 - Never or almost never have the symptom
- 1 - Occasionally have it, effect is not severe
- 2 - Occasionally have it, effect is severe
- 3 - Frequently have it, effect is not severe

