- 4- Frequently have it, effect is severe

Difficulty breathing

Digestive Tract

Rate the Symptom

- 0 - Never or almost never have the symptom
- 1 - Occasionally have it, effect is not severe
- 2 - Occasionally have it, effect is severe
- 3 - Frequently have it, effect is not severe
- 4- Frequently have it, effect is severe

Nausea or Vomiting

- 0 - Never or almost never have the symptom
- 1 - Occasionally have it, effect is not severe
- 2 - Occasionally have it, effect is severe
- 3 - Frequently have it, effect is not severe
- 4- Frequently have it, effect is severe

Diarrhea

- 0 - Never or almost never have the symptom

Constipation

Rate the Symptom

- 1 - Occasionally have it, effect is not severe
- 2 - Occasionally have it, effect is severe
- 3 - Frequently have it, effect is not severe
- 4- Frequently have it, effect is severe

Bloated feeling

- 0 - Never or almost never have the symptom
- 1 - Occasionally have it, effect is not severe
- 2 - Occasionally have it, effect is severe
- 3 - Frequently have it, effect is not severe
- 4- Frequently have it, effect is severe

Belching

- 0 - Never or almost never have the symptom
- 1 - Occasionally have it, effect is not severe
- 2 - Occasionally have it, effect is severe
- 3 - Frequently have it, effect is not severe
- 4- Frequently have it, effect is severe

Passing gas

- 0 - Never or almost never have the symptom
- 1 - Occasionally have it, effect is not severe
- 2 - Occasionally have it, effect is severe
- 3 - Frequently have it, effect is not severe
- 4- Frequently have it, effect is severe

Heartburn

- 0 - Never or almost never have the symptom
- 1 - Occasionally have it, effect is not severe
- 2 - Occasionally have it, effect is severe
- 3 - Frequently have it, effect is not severe
- 4- Frequently have it, effect is severe

Intestinal or stomach pain

- 0 - Never or almost never have the symptom
- 1 - Occasionally have it, effect is not severe

- 2 - Occasionally have it, effect is severe
- 3 - Frequently have it, effect is not severe
- 4- Frequently have it, effect is severe

Joints/Muscle

Rate the Symptom

Pain or aches in joints

- 0 - Never or almost never have the symptom
- 1 - Occasionally have it, effect is not severe
- 2 - Occasionally have it, effect is severe
- 3 - Frequently have it, effect is not severe
- 4- Frequently have it, effect is severe

Arthritis

- 0 - Never or almost never have the symptom
- 1 - Occasionally have it, effect is not severe

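### All six named side effects are already rated on the symptom questionnaire at baseline, Visit 1 and Visit 2, but the adverse-effect history makes no use of those ratings

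*Protocol*

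**What the plan says.** Monitoring/Reporting names the expected harms: "Possible side effects include but are not limited to: diarrhea, constipation, nausea, vomiting, bloating or headache". The Background lists the symptoms of SIBO, again as an open list, and includes "abdominal pain, discomfort, bloating, cramping, flatulence, diarrhea, constipation, eructation, and low serum B12". The inclusion criteria refer back to those symptoms, so patients can enter with one or more of the expected side effects already present.

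On collection, Study Procedures states for Visit 1: "Patients will be asked to report their compliancy with the supplement protocol and low FODMAP diet and describe adverse effects". Visit 2 asks for adverse effects in the same open way. Between visits patients may report events by phone, and clinic staff may contact them when necessary and record events in the file.

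The questionnaire is completed at Visit 0 (baseline), Visit 1 and Visit 2. Its stated use is in Data Management: "completed Medical Symptom Questionnaire will be compared pre- and post-treatment to determine the efficacy of the supplement therapy". The protocol gives it no safety use and does not say how the adverse-effect history should treat a symptom that was present at baseline and has become worse.

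**The concern.** When an expected side effect is also a symptom of the disease, an open question about adverse effects leaves the patient to decide which is which. A patient who entered with bloating and now has more of it may put it down to SIBO and not mention it. No control group shows what the disease would have done unaided, so the patient's own baseline is the only available reference. That reference is collected, but nothing links it to the adverse-effect history.

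The tolerability record is at stake: some worsening on treatment may never be considered as a possible harm. The protocol also foresees use of favorable results in advertising, so an incomplete record would reach beyond the clinic.

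**Working it through.** The protocol gives no figure to reproduce on this point. The check matches lists, then looks at timing, then at the item scale.

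**Step 1. Side effects against questionnaire items and SIBO symptoms** (Monitoring/Reporting, Appendix B, Background).

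| Named side effect | Item in Appendix B | On the SIBO symptom list? |
|---|---|---|
| Diarrhea | Diarrhea | Yes |
| Constipation | "Constipation" | Yes |
| Bloating | "Bloated feeling" | Yes |
| Nausea | "Nausea or Vomiting" (shared) | No |
| Vomiting | "Nausea or Vomiting" (shared) | No |
| Headache | Headache | No |

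Side effects with an item: 6 of 6. Distinct items: 6 − 1 = 5, because nausea and vomiting share one and cannot be told apart on the form. Overlap with the SIBO list: 3 of 6.

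**Step 2. Timing** (Study Procedures, Appendix C).

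- Visit 1 is at about 4 weeks. The Weeks 2–5 block of the schedule contains all six products; the first of them to finish ends 2 days into week 5, so at 4 weeks all six are scheduled.
- Visit 2 waits for the result of a breath test done within 2 weeks of completing the therapy.
- The supplement course is 8 weeks and the whole investigation is estimated at 12. If the 12 weeks are counted from the start of treatment (an assumption), Visit 2 may fall up to 12 − 8 = 4 weeks after the course ends.

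The Visit 1 form is therefore the only scheduled structured symptom record taken during the 8-week course. A symptom that rose during treatment and settled afterwards need not show in a comparison of baseline with Visit 2.

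**Step 3. What the item scale would show.** Each item runs from 0 to 4 and combines frequency with severity: 1 is occasional and not severe, 2 is "2 - Occasionally have it, effect is severe", 3 is frequent and not severe, 4 is frequent and severe.

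- Possible changes between two different levels: 5 × 4 = 20.
- Changes in which neither frequency nor severity improves and at least one worsens: the score rises every time, with no exceptions.
- Changes in which the effect becomes severe: 0→2, 0→4, 1→2, 1→4, 3→2 and 3→4, six in all. The score falls in one of them, 3→2, and there frequency improves.

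The five items would thus normally show worsening as a higher score. Looking only for higher scores would miss one kind of change, 3→2, which is why severity should also be looked at separately.

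**The case against.** The strongest reply is that open questioning is an accepted way to collect adverse effects and that the protocol does more than wait for complaints. Patients are actively asked at both visits, staff may phone them, and the synopsis has the investigator re-assess symptoms after treatment. This stands: collection is not left wholly to the patient's initiative, and the open question is not an error. But the post-treatment re-assessment is framed as an outcome assessment and gives no week-4 safety review, and none of these provisions refers the history to the baseline ratings.

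A second reply is that tables of the week-4 form belong in a statistical analysis plan, which may exist. That also stands: the absence of such a table here is no finding. How the adverse-effect history is taken at a visit is a protocol matter.

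A third is that comparing with baseline cannot separate harm from disease without a control group. This is true. It is also why treating every rise in score as an adverse event would be wrong: that would exchange under-recording for over-recording.

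A reader might infer three stronger claims, which the documents do not support:

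- **That harm would be scored as benefit.** On a single item this needs the 3→2 change, where frequency improves, and a scoring rule that the protocol does not state.
- **That the termination rule is undermined.** The rule counts withdrawals attributed to adverse events. Nothing in the protocol shows how a withdrawal would be classified, so the link is conjecture, and comparing questionnaires would not settle it.
- **That the heart and lung items also need safety review.** They are on a general questionnaire but are not among the named side effects.

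**Conclusion.** The point holds as an inexpensive improvement. The protocol contains no contradiction or wrong figure here. All 6 named side effects have an item already rated at all three time points, and 3 of the 6 are also disease symptoms, yet those ratings have no stated role in the adverse-effect history. Worsening of a bowel symptom present at baseline, including worsening that resolves before Visit 2, can therefore go unrecorded as a possible harm.

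How often this would happen cannot be calculated: the protocol gives no rates for these symptoms or side effects. The conclusion assumes that some patients enter with the overlapping symptoms, as the inclusion criteria suggest, and that the history is taken as Study Procedures describes, without the completed form in view.

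**What to change.** In Study Procedures, for Visits 1 and 2, add that when taking the adverse-effect history the investigator compares the completed questionnaire with the patient's baseline on five items: headache, nausea or vomiting, diarrhea, constipation and bloated feeling. The investigator asks about any item that is higher than at baseline or has moved from a not-severe to a severe category, then documents whether it is recorded as an adverse event and why. The decision stays a documented judgment, with no automatic rule.

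In Data Management, add that changes from baseline on these items at week 4 and at Visit 2 are reported descriptively beside the effects that patients described, with frequency and severity shown separately.

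The change needs no new data, visit or staff: it costs a few minutes per visit and one descriptive table for about 10 patients. Some ordinary SIBO fluctuation will be listed, and the report should say that without a control group the table does not establish cause.

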The treatment of SIBO frequently consists of antibiotic therapy. Rifaximin is a poorly absorbed antibiotic with bacteriocidal activity against enteropathogens and is widely prescribed for the treatment of SIBO.³ Nevertheless, both patients and practitioners frequently turn to complementary and alternative medicine, due to the adverse effects associated with antibiotic use and the recurrent nature of SIBO. In 2014, a retrospective study (Chedid et al.) found that the efficacy of a particular herbal therapy was comparable to Rifaximin treatment.³ However, both treatment

options demonstrated a response rate of less than 50%. This investigation will test a more comprehensive, supplement-based therapy in hopes of achieving a greater response rate.

Objectives

This investigation aims to determine the efficacy of a supplement protocol in combination with a low FODMAP diet for the treatment of small intestinal bacterial overgrowth (SIBO).

Patient Selection

Patients diagnosed with SIBO at [name] clinic will be offered the opportunity to enroll in this study as a theoretical treatment option for SIBO. Other treatment options will be discussed with the patient. Enrolled patients must satisfy the following inclusion and exclusion criteria:

Inclusion criteria: A positive diagnosis of SIBO, which will be defined by 1) presentation of the aforementioned symptoms and 2) positive results of a lactulose breath test. Positive breath test results will be defined as an increase in hydrogen of 20 ppm or more and/or an increase in methane of 12 ppm or more compared to baseline by 90 minutes.

Exclusion criteria: 1) Use of prescription antibiotics or antifungals within the past 4 weeks. 2) Younger than 18 or older than 85 years of age 3) Pregnant or breast-feeding 4) Major drug-supplement interactions between essential medication and the proposed supplement therapy. 5) A known allergy to one or more of the ingredients in the supplement therapy. 6) Has been diagnosed and treated for SIBO within the past 6 months. 7) Has undergone a colonoscopy or barium enema within the past 4 weeks. 8) Has an allergy to lactulose. 9) Has diabetes mellitus.

Study Procedures

The supplement protocol is designed to take 8 weeks. Due to the delay in receiving and interpreting test results, the investigation, in its entirety, is estimated to take 12 weeks.

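### The pre/post breath-test change cannot determine efficacy: its baseline is the test that qualified the patient, there is no control group, and the protocol states no such limit

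*Protocol*

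**What the plan says.** **Entry.** Under Patient Selection, inclusion needs "presentation of the aforementioned symptoms" and a positive lactulose breath test, defined as "an increase in hydrogen of 20 ppm or more and/or an increase in methane of 12 ppm or more" over baseline by 90 minutes.

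**Timing of the tests.** Under Study Procedures, the breath test is prescribed at Visit -1 when history and symptoms suggest the condition. At Visit 0 the investigator "will assess the results of the breath test and confirm or deny the diagnosis of SIBO". At Visit 1: "Patients will be provided with the second lactulose breath test kit", for use within two weeks of finishing therapy. Only these two tests are scheduled.

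**Design.** From the Study Synopsis: "The study is designed as a prospective, open label investigation", with an estimated 10 patients, and "No control group will be assigned".

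**Analysis and use.** Under Data Management, breath tests and questionnaires "will be compared pre- and post-treatment to determine the efficacy of the supplement therapy". Then: "The significance of the change in breath test scores will be determined if the final sample size permits such analysis". Intended Use of the Data says that the data serve to determine efficacy and that, if the therapy proves efficacious, the results go into print and digital advertising. It does not say what would count as efficacious.

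**The concern.** A patient enters because a gas rise is above a cut-off, and that same reading then serves as the baseline for the change. Part of any high reading is chance variation, which does not carry over to the next test. The qualifying gas is therefore expected to be lower on retest even if the therapy does nothing, unless the two readings agree perfectly. A paired test of the change addresses the hypothesis of no change, not the hypothesis of no treatment effect. With no control group and no second pre-treatment test, the data cannot separate the two.

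The protocol nevertheless gives this comparison the task of determining efficacy and links the result to advertising. It says nowhere that selection on the baseline limits the conclusion. What is at stake is an efficacy statement, possibly made in public, that selection alone could have contributed to or produced.

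**Working it through.** **1. Is the baseline the qualifying test?** Yes. The test read at Visit 0 settles the diagnosis and hence entry. The post-treatment kit is called the second, and the Synopsis describes it as a repeat of the diagnostic test. No other reading is available as a pre-treatment value.

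**2. Can the size be computed from the protocol?** No. The protocol gives no standard deviation, no retest correlation and no share of tested patients who are positive. It names no test or significance level, and it does not say how a breath test score is derived. There is no stated figure to reproduce. Everything below is illustration.

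**3. Inputs.** From the protocol: 10 patients, entry on exceeding a cut-off, no control. Assumed: one qualifying gas, no treatment effect, same mean and SD at both tests, retest correlation r from 0.9 down to 0.3, share positive p from 90% down to 31%, and a two-sided 5% paired t-test, so that the nominal chance of a significant fall is 2.5%.

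**4. Expected untreated change.** For normal values, with cut-off c in SD units, density φ and share positive p:

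mean change = −(1 − r) × φ(c) / p

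- p = 0.90, r = 0.9: −0.1 × 0.1755 / 0.90 = −0.019 SD
- p = 0.50, r = 0.7: −0.3 × 0.3989 / 0.50 = −0.24 SD (if the SD were 20 ppm, −4.8 ppm)
- p = 0.31, r = 0.3: −0.7 × 0.353 / 0.31 = −0.80 SD

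**5. Chance of a significant fall with no treatment effect** (simulation, normal values, n = 10):

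| Share positive | r = 0.9 | r = 0.7 | r = 0.5 | r = 0.3 |
|---|---|---|---|---|
| 90% | 3.3% | 4.0% | 4.6% | 5.0% |
| 70% | 5.0% | 8.1% | 11.2% | 14.4% |
| 50% | 7.4% | 14.8% | 23.1% | 32.3% |
| 31% | 11.0% | 26.2% | 42.6% | 59.6% |

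An exact signed-rank test (nominal 2.4%) gives 3.2% to 57.6% over the same settings.

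**6. Skewed values** (log-normal, t-test on the raw scale; first figure r = 0.9, second r = 0.3):

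- log-SD 0.5: 2.7% and 3.9% at 90% positive; 9.0% and 47.8% at 31% positive
- log-SD 1.0: 1.6% and 2.4% at 90% positive; 6.4% and 34.3% at 31% positive
- log-SD 1.0, 70% positive, r = 0.9: 2.5%, again no inflation

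**7. How far the range depends on the settings.** A harsher normal setting (mean 10 ppm, SD 10 ppm, cut-off 20 ppm, r = 0.3), where the cut-off lies one SD above the mean, reaches 85%. The upper end is therefore set by the assumptions chosen, not by the protocol.

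**8. The gas that did not qualify the patient.** Entry can be on either gas. Suppose 5% of tested patients are methane-positive and 50% to 70% hydrogen-positive, and each gas is tested in all enrolled patients. Methane then shows a significant fall in 1.8–2.1% of no-effect trials at cross-gas correlation −0.3, 2.9–3.5% at 0, and 4.6–10.7% at 0.5. Hydrogen in the same trials shows one in 7.1–31.2%. The expected fall belongs to the qualifying gas.

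**9. The questionnaire.** No questionnaire score is an entry cut-off. It is completed at Visit 0 after consent, and many items (eyes, ears, skin, mind) are not the symptoms for which patients are selected. It is still self-report by patients who know they are treated and who were chosen for having symptoms, with no comparator.

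**The case against.** **No decision rule is stated.** A reader might infer that a significant fall will, alone, be declared proof of efficacy. The protocol does not say so. It takes breath tests and questionnaires together, makes the significance test conditional on the final sample size, and leaves efficacious undefined. That stands. What remains is that the uncontrolled comparison is itself given the purpose of determining efficacy, whether or not a test is run.

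**It is a declared pilot.** An uncontrolled, open-label study of about 10 patients is legitimate, and choice of test and reporting detail may sit in an analysis plan that is not shown. That also stands, and neither is criticised here. But the protocol itself fixes the baseline, the absence of a control, the efficacy purpose and the advertising use.

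**The inflation may be negligible.** A reader might infer from the upper figures that the false-positive rate is seriously inflated. The documents do not support that. The breath test is prescribed only when history and symptoms point to the condition, so the share positive may be high, which favours the mild end. Some skewed settings show no inflation.

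**The questionnaire is not the selecting measurement.** Correct. To treat it as equally distorted by the entry rule would overstate the case. It is exposed to open-label reporting and natural fluctuation instead.

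**Conclusion.** The point holds as a limit on the conclusion. The baseline is the qualifying test, there is no second pre-treatment test and no control group, so some fall in the qualifying gas is expected without treatment, and the pre/post change cannot determine efficacy as the protocol says it will. That reasoning needs only a retest correlation below 1.

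The size is unknown. Under the assumed one-gas settings with 10 patients and 31% to 90% of tested patients positive, the chance of a significant fall without any effect runs from about 2% to about 60%, against a nominal 2.5%. The range rests wholly on assumed retest correlation, share positive and distribution, and on a paired test that the protocol does not name. The sponsor should correct the wording. Nothing here shows that the pilot is unsound as a pilot, or that a fall, if seen, would be due to selection alone.

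**What to change.** **Data Management.** Replace both sentences on the pre/post comparison and its significance. Changing only the second would leave the efficacy purpose in the first, in contradiction with the new text. Suggested wording:

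> *Changes from before to after treatment in lactulose breath test scores and in Medical Symptom Questionnaire scores will be reported descriptively with 95% confidence intervals. Because patients were selected on the pre-treatment breath test, the study is open label and there is no control group, some improvement is expected without treatment; neither the changes nor an interval that excludes zero will be taken as showing efficacy.*

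The last clause is needed because the interval is centred on the same biased change. Under the one-gas normal settings it excludes zero in 5.2% to 59.6% of no-effect trials.

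**Intended Use of the Data.** State that the data will describe changes during therapy and inform a controlled study, and remove or correspondingly limit the sentence on advertising.

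**Objectives and Study Synopsis.** Make the stated aim consistent with this.

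**Cost.** Wording only, with no new visits or data. The price is a weaker efficacy statement. The change limits the conclusion but does not remove the bias. Removing the part due to selection would need a second pre-treatment breath test not used for entry, or a control group. The second test alone would still leave other untreated change unseparated.
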